**This protocol has regard for the Health Research Authority guidance and order of content.**

## VERSION CONTROL

Amendment no.	Protocol version no.	Date issued	Author(s) of changes	Details of changes made
1.0	2.0	28 July 2016	[name]	
Throughout: Correction of typographical mistakes.
 
6.1: Addition to inclusion criterion 3 of “OR deemed unsuitable for step two within an IAPT service”.
 
7: Revised wording to clarify that 6 – 8 week waiting list is a minimum.
 
7.1: Revised identification process to remove follow up letter for non-responders.
 
7.4: Clarification of expectation of morning device use.
 
9.2/3: Clarification that AEs and SAEs must be recorded in the CRF.
 
11.2: Clarification that recruitment window is 6 months and not 12 months.
 
12.1: Clarification of anticipation that CRF will act as source documentation.
 
12.2: Clarification of email data transfer within 3 working days.
 
Appendix B: Revised structure of CSRI but no change to content.
 
Appendix C: Inclusion of EQ-5D-5L assessment tool.

## STUDY SUMMARY

Full Study Title	Clinical and cost effectiveness of Alpha-Stim AID Cranial Electrotherapy Stimulations (CES); a naturalistic study in patients with a primary working diagnosis of moderate-to-severe generalised anxiety disorder (GAD) who did not improve with low intensity psychological therapy intervention.
Short Study Title	Clinical and cost effectiveness of Alpha-Stim AID CES.
Lay Study Title	Using a safe electronic device to help patients with anxiety disorder who did not improve with low intensity psychological therapy intervention.
Study Design	Single-centre, naturalistic post-market clinical study of one CE marked device within intended purpose over 24 week follow up period.
Study Participants	Patients seen within the three teams comprising Leicestershire and Rutland Improving Access to Psychological Therapies (IAPT) service (part of Nottinghamshire Healthcare NHS Foundation Trust) with a primary working diagnosis of moderate-to-severe generalised anxiety disorder (GAD) who did not improve (continued to have a primary working diagnosis of moderate-to-severe GAD) with previous low intensity psychological therapy intervention.
Planned Sample Size	120

Study Duration Per Participant	24 weeks	
Planned Enrolment Period	6 months from 01 September 2016 to 01 March 2017	
Planned Study End Date	01 September 2017	
Study End Definition	Last Participant Last Visit	
	Objectives	Outcome Measures
Primary	
The primary objective of this study is to evaluate the clinical effectiveness of treatment with Alpha-Stim AID Cranial Electrotherapy Stimulations (CES) for participants with a primary working diagnosis of generalised anxiety disorder (GAD), as defined by the NHS IAPT service in terms of reliable improvement, clinically significant improvement, and recovery, from baseline to week 24, following previous treatment with low intensity psychological therapy intervention.
	
GAD-7
 
See Appendix A
 
The GAD-7 is a participant-reported screening tool and severity measure for generalised anxiety disorder (GAD).
 
Reliable improvement is defined as participants who reach a score reduction of 5 or more from baseline to week 24. Such a reduction amounts to a clinically important change.
 
Some reliable improvement is defined as participants who reach a score reduction of 1 – 4 from baseline to week 24.
 
No reliable improvement is defined as participants who reach no score reduction from baseline to week 24.
 
Clinically significant improvement is defined as participants with a score of 10 or more at baseline, who reach 9 or fewer by week 24.
 
Recovery is defined as participants with a score of 10 or more at baseline, who reach 7 or fewer by week 24.

Secondary	
The secondary objective of this study is to evaluate the cost effectiveness of treatment with
	
Client Service Receipt Inventory (CSRI)

	
Alpha-Stim AID Cranial Electrotherapy Stimulations (CES) for participants with a primary working diagnosis of generalised anxiety disorder (GAD), in terms of health and social care service cost, and patient cost, from baseline to week 24, following previous treatment with low intensity psychological therapy intervention.
	
See Appendix B
 
The CSRI, adapted for use for anxiety disorders in primary care and community settings, is a measure of the full health and social care cost and patient cost of treatment.
 
The endpoint will be the cost impact from baseline to week 24.
 
EQ-5D-5L
 
See Appendix C
 
The EQ-5D-5L is a participant-reported measure of health utility and quality of life used by NICE to generate QALYs for cost effectiveness assessments. The EQ-5D-5L uses 6 items.
 
The endpoint will be the change in EQ-5D-5L for participants from baseline to week 24.
 
Work and Social Adjustment Scale (WASA)
 
See Appendix D
 
The WASA scale is a participant-reported measure of work and social function. The WASA scale uses 5 items.
 
The endpoint will be the change in WASA scale score for participants from baseline to week 24.

Tertiary
	
The tertiary objective of this study is to evaluate the clinical effectiveness of treatment with Alpha-Stim AID Cranial Electrotherapy Stimulations (CES) for depression and insomnia in participants with a
	
PHQ-9
 
See Appendix E
 
The PHQ-9 is a participant-reported measure of depressive symptomatology.

	
primary working diagnosis of generalised anxiety disorder (GAD), in terms of reliable improvement, clinically significant improvement, and recovery, from baseline to week 24, following previous treatment with low intensity psychological therapy intervention.
	
Reliable improvement is defined as participants who reach a score reduction of 6 or more from baseline to week 24.
 
Clinically significant improvement is defined as participants with a score of 10 or more at baseline, who reach 9 or fewer by week 24.
 
Recovery is defined as participants with a score of 11 or more at baseline, who reach 8 or fewer by week 24.
 
Athens Insomnia Scale
 
See Appendix F
 
The Athens Insomnia Scale is a participant-reported measure of sleep difficulty.
 
Reliable improvement has no current, standardised definition, and so in this study, will be defined as participants who reach a score reduction of 50% or more from baseline to week 24.
 
Clinically significant improvement is defined as participants with a score of 6 or more at baseline, who reach 5 or fewer by week 24.
 
Recovery is defined as participants with a score of 6 or more at baseline, who reach 4 or fewer by week 24.

Medical Device
	
Alpha-Stim AID Cranial Electrotherapy Stimulations (CES) medical device, used within intended purpose (for the treatment of anxiety, depression and insomnia), under CE marking valid 12 April 2016 – 12 September 2020.
	

	See Appendix H
Treatment Procedure	
60-minute self-directed Alpha-Stim AID CES treatment sessions undertaken at participant's home, on a daily basis for 6 weeks for all participants. During this 6-week period, participants will be on the waiting list for high intensity psychological therapy intervention.
 
Following 6 weeks of Alpha-Stim AID CES treatment, participants have the option to receive a further 6 weeks of treatment, which is likely to coincide with start of high intensity psychological therapy intervention as clinically indicated.
 
Following a maximum of 12 weeks' treatment with Alpha-Stim AID CES, all participants will cease to receive treatment on study.
 
Participants will have 1x additional visit in clinic at baseline, followed by 5 additional visits via telephone at week 4, 6, 8, 12 and 24.
 
All participants will continue to receive standard care assessment, as undertaken by the NHS IAPT service, standard care high intensity psychological therapy intervention as clinically indicated and provided by the NHS IAPT service, and standard care pharmacological treatment as prescribed by the participant's GP. Participation in this study will not influence nor compromise standard care treatment – all study procedures are additional to standard care. Participation in the study will have no impact upon the duration of the waiting time for high intensity psychological therapy intervention.

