#### 3.2 Secondary objectives

The secondary objective of this study is to evaluate the cost effectiveness of treatment with Alpha-Stim AID cranial electrotherapy stimulations (CES) for participants with a primary working diagnosis of generalised anxiety disorder (GAD), in terms of health and social care service cost, and patient cost, over the previous 12 weeks, from baseline to week 24, following previous treatment with low intensity psychological therapy intervention.

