#### 3.5 Secondary outcome measures

The secondary objective will be measured using the Client Service Receipt Inventory (CSRI), adapted for use for anxiety disorders in primary care and community settings, which is a measure of the full health and social care cost and patient cost of treatment. Additionally, the objective will be measured using the EQ-5D-5L, which is a participant-reported measure of health utility and quality of life used by NICE to generate QALYs for cost effectiveness assessments, and uses 6 items. Finally, the objective will be measured using the Work and Social Adjustment Scale (WASA) which is a participant-reported measure of work and social function, and uses 8 items.

- The outcome measure for **CSRQ** is the change in cost impact for previous 12 weeks from baseline to week 24.
- The outcome measure for **EQ-5D-5L** is the change for participants from baseline to week 24.
- The outcome measure for **WASA** is the change for participants from baseline to week 24.

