### EQ-5D-5L

*See Appendix C*

The EQ-5D-5L is a participant-reported measure of health utility and quality of life used by NICE to generate QALYs for cost effectiveness assessments. The EQ-5D-5L uses 6 items, covering the categories of mobility, self-care, usual activities, pain/discomfort, anxiety/depression and a visual analogue score of health state.

The research nurse will administer the EQ-5D-5L and record the data either directly into the electronic patient record (PCMIS) if available (and therefore the PCMIS record will act as source data), or into a Case Report Form (CRF) if not available (and therefore the CRF will act as source data) and then transpose the data into PCMIS or scan the CRF into the electronic file.

It is anticipated that this assessment will take approximately 5 minutes.

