## **7.5 Study assessments**

At baseline, participants will agree with the research nurse a convenient time and date for the visits undertaken via telephone. Visits should be undertaken within 5 calendar days of the exact date.

Additional visits are undertaken at 4 weeks post baseline, 6 weeks post baseline, 8 weeks post baseline, 12 weeks post baseline and 24 weeks post baseline.

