#### **Visit 6: Week 24 (plus or minus 5 calendar days)**

The research nurse will telephone call the participant and undertake the following assessments:

- GAD-7
- EQ-5D-5L
- CSRI

- WASA
- PHQ-9
- Athens Insomnia Scale

The research nurse will administer these and record the data either directly into the electronic patient record (PCMIS) if available (and therefore the PCMIS record will act as source data), or into a Case Report Form (CRF) if not available (and therefore the CRF will act as source data) and then transpose the data into PCMIS or scan the CRF into the electronic file.

It is anticipated that these assessments will take approximately 30 minutes in total.

This is the end of study visit, after which the participant will cease communication with the research nurse.

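### The EQ-5D-5L endpoint uses only baseline and week 24, so the six scheduled measurements yield no QALY for the cost-effectiveness objective

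*Combined protocol and SAP*

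**What the plan says.** The Study Summary, under the secondary outcomes, states: "The endpoint will be the change in EQ-5D-5L for participants from baseline to week 24". Section 3.5 repeats it: the EQ-5D-5L outcome "is the change for participants from baseline to week 24".

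Section 3.2 gives the objective that this outcome serves. It opens "The secondary objective of this study is to evaluate the cost effectiveness of treatment with" the device, and frames the evaluation in terms of service cost and patient cost. Section 3.5 introduces EQ-5D-5L as a measure of "health utility and quality of life used by NICE to generate QALYs for cost effectiveness assessments", and the Study Summary and section 7.4 describe it in the same way. Section 2 says the evidence is meant for a NICE appraisal that needs an economic assessment.

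On collection, section 7.4 says for the baseline visit: "The research nurse will administer the EQ-5D-5L and record the data". Section 7.5 places the later visits at "4 weeks post baseline, 6 weeks post baseline, 8 weeks post baseline, 12 weeks post baseline and 24 weeks post baseline" and lists EQ-5D-5L at each of them. The section 7.6 table marks it at all six time points. Device use stops at week 6, or at week 12 for those who extend.

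The analysis plan in section 11.3 consists of the mean and SD at each visit. No value set, QALY calculation or area under the curve is specified anywhere. The endpoint also does not say whether it refers to the index value or to the visual analogue score that section 7.4 counts as the sixth item.

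**The concern.** A QALY is the area under the utility curve over time. The difference between the first and last values is a different quantity and cannot be converted into one without assuming the whole path between them. The last value is taken 12 weeks after device use ends for participants who extend, and 18 weeks after for those who do not. The four measurements at weeks 4, 6, 8 and 12 carry no weight in the defined endpoint, although the first two fall within everyone's planned device period.

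At stake is the health side of the cost-effectiveness result. The same week-24 change is compatible with quite different health gains, and the endpoint can order two utility profiles in the opposite way to their QALYs. If a QALY is wanted later for NICE, its method would be chosen after the data have been seen.

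**Working it through.** The plan gives no EQ-5D-5L effect size, SD or QALY figure, so there is nothing to reproduce. The check compares the stated endpoint with a QALY for simple profiles.

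**Inputs.** Visit times 0, 4, 6, 8, 12 and 24 weeks (sections 7.5 and 7.6). Let u be the change in utility from the participant's own baseline. The gain g is not in the documents; 0.03 to 0.15 is assumed.

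**Formulas.** Stated endpoint = u(24) − u(0). QALY gain = sum over intervals of (interval length) × (mean of the two end values), divided by 52.

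**Results.**

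| Profile at weeks 0, 4, 6, 8, 12, 24 | Endpoint | Six-visit QALY gain | Two-point interpolation |
|---|---|---|---|
| Faded: 0, g, g, g, g, 0 | 0 | (2+2+2+4+6)g/52 = 16g/52 = 0.308g | 0 |
| Early fade: 0, g, g, 0, 0, 0 | 0 | (2+2+1)g/52 = 5g/52 = 0.096g | 0 |
| Late: 0, 0, 0, 0, 0, g | g | 6g/52 = 0.115g | 12g/52 = 0.231g |
| Held: 0, g, g, g, g, g | g | (2+2+2+4+12)g/52 = 22g/52 = 0.423g | 12g/52 = 0.231g |

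The late and held profiles share an endpoint but differ by a factor of 22/6 = 3.7 in QALYs. The faded profile has a lower endpoint than the late one but a larger QALY gain.

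**Dependence on the unobserved half.** No visit falls between weeks 12 and 24, and 6/52 of the faded figure is the assumed straight-line decline over that stretch. If the gain is lost just after week 12, the area is 10g/52 = 0.19g. If it is lost just before week 24, the area approaches 22g/52 = 0.42g. The late profile has the same uncertainty: from near 0 if the gain appears just before week 24, to 12g/52 = 0.23g if it appears just after week 12. The reversed ordering therefore holds under linear interpolation and most other paths, but not at every extreme (0.19g against 0.23g).

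**Scale.** For the faded profile with linear decline:
- g = 0.03: 16 × 0.03/52 = 0.009
- g = 0.05: 0.015
- g = 0.10: 0.031
- g = 0.15: 0.046

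For the early fade, the range over g = 0.03 to 0.15 is 0.003 to 0.014. All are gains over the participant's own baseline.

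**The case against.** Four points can fairly be made for the plan.

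1. A reader might infer that a gain during device use would be invisible. Section 11.3 does not support that: means and SDs are promised at every visit, so the gain would show at weeks 4 to 12. Because the trapezoid rule is linear, a mean QALY change even follows from the visit mean index values if data are complete and visits fall on their nominal dates. This stands in part. The precision does not follow, because the SD of a participant's QALY depends on the correlations between visits, which visit SDs do not give.

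2. A reader might infer that the plan promises QALYs and then fails to deliver them. It does not promise them. The text describes what NICE does with the instrument, the objective is framed in terms of cost, and the only economic argument, in section 11.1, is a cost offset based on GAD-7 response. This stands. The mismatch is with the stated NICE purpose, not with a commitment to a QALY result.

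3. A reader might infer that the study sets out to value the device period alone. Every objective runs to week 24, so a week-24 outcome is consistent with the stated aims. This stands as a reason to keep that outcome, but it does not make the outcome a measure of health gained over the 24 weeks.

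4. Changing EQ-5D-5L alone would not create a matched pair, because the section 3.5 cost outcome is itself a change between 12-week windows and not a total. This is correct, and the fix has to cover both sides.

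**Conclusion.** The concern holds in a limited form. The EQ-5D-5L endpoint is a two-point change serving a cost-effectiveness objective, and the plan pre-specifies no QALY although the schedule collects what is needed for one. A gain held to week 12 and fully lost by week 24 scores zero on the endpoint against 0.31g QALY (0.19g to 0.42g by timing of the loss), or 0.009 to 0.046 QALY for an assumed g of 0.03 to 0.15 under linear decline. The zero is exact only for a full return to baseline; a partial fade is understated. For the same week-24 change of g, the QALY gain is 0.115g or 0.42g according to whether the gain is first seen at week 24 or is present from week 4.

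These figures assume linear change between visits and an assumed size of g. With one arm, entry restricted to GAD-7 of 10 or more, and high intensity therapy possible after the waiting period, the QALY would be gain over own baseline. It would not show what the device adds to usual care.

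**What to change.** In the Study Summary and section 3.5, with a matching line in section 11.3:

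- Define the EQ-5D-5L economic endpoint as QALYs from day 1 to week 24: the area under the index-value curve through all six visits by the trapezoid rule at actual visit dates, minus baseline utility held constant, with a confidence interval.
- Name the value set.
- Keep the week-24 change as a supporting result.
- State a rule for missed intermediate calls.
- Add a sensitivity analysis for weeks 12 to 24. For values u(12) and u(24), the contribution is 12u(24)/52 if the change comes just after week 12, 6(u(12)+u(24))/52 if it is linear, and approaches 12u(12)/52 if it comes just before week 24.
- Pair the QALYs with total CSRI cost over the same 24 weeks, from the week-12 and week-24 recalls. The study flow chart shows the middle CSRI at week 6, while sections 7.5 and 7.6 put it at week 12. These must be reconciled, because the pairing relies on the week-12 recall.
- State that, with one arm, the result is gain over own baseline and not over usual care.

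The cost is protocol wording and a short calculation on data already scheduled, with no added visits. The drawback is that a participant who misses an intermediate call needs interpolation or imputation, which the two-point change would not require.

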**FUNDING AND SUPPORT IN KIND**

FUNDER	FINANCIAL AND NON FINANCIAL SUPPORT GIVEN
The Microcurrent Site Limited	
60 Alpha-Stim AID CES devices loaned to Nottinghamshire Healthcare NHS Foundation Trust for duration of study. Should all 60 devices be in use by participants concurrently, additional devices may be loaned to the Trust.
 
Consumables will be provided to the Trust, including AAA batteries, pregnancy testing kits, cleaning materials, conduction fluid and electrode pads.
 
Total funding of approximately £38,000.00 to Nottinghamshire Healthcare NHS Foundation Trust for study delivery costs.

## **ROLE DELEGATION**

### **SPONSOR: Electromedical Products International, Inc**

Under the Research Governance Framework for Health and Social Care 2005, Electromedical Products International Inc is the legal sponsor of this research study. Electromedical Products International Inc retains responsibility for all legally mandated roles of a sponsor of clinical research, but has delegated a number of roles to the organisations listed below.

### **LEGAL REPRESENTATIVE AND CONTRACT RESEARCH ORGANISATION: The Microcurrent Site Limited**

Under the Research Governance Framework for Health and Social Care 2005, a sponsor incorporated outside of the United Kingdom must appoint a legal representative incorporated in the United Kingdom for service of documents. Given that Electromedical Products International Inc is incorporated in the United States of America, The Microcurrent Site Limited will fulfil the role of legal representative.

In this role as legal representative, The Microcurrent Site Limited is also undertaking the following roles on behalf of the sponsor:

- Point of contact for study conduct queries
- Upload of accrual data to the NIHR CRN Portfolio database (CPMS)
- Oversight of conduct and delivery
- Archiving
- Manuscript writing
- Dissemination of results

### **FUNDER: The Microcurrent Site Limited**

The Microcurrent Site Limited is responsible for the provision of funding and will process and pay invoices from the NHS research site, and is also responsible for the provision of loaned medical devices and consumables.

### **CONTRACTED ORGANISATION: Research Applications Limited**

Research Applications Limited is responsible for creation and submission of study documents to the Health Research Authority (HRA) for Research Ethics Committee (REC) favourable opinion, HRA Approval; submission to the National Institute for Health Research Clinical Research Network (NIHR CRN) Portfolio; and submission to the NHS R&D department of Nottinghamshire Healthcare NHS Foundation Trust for confirmation of capacity and capability. No application to the Competent Authority is required.

## LIST OF ABBREVIATIONS

AE	Adverse Event
CA	Competent Authority (MHRA)
CBT	Cognitive Behavioural Therapy
CI	Chief Investigator
CE	Conformitee Europeenee
CES	Cranial Electrotherapy Stimulations
CPMS	Central Portfolio Management System
CRF	Case Report Form
CRN	Clinical Research Network
CRO	Contract Research Organisation
CSRI	Client Services Receipt Inventory
EU	European Union
FDA	Food and Drug Administration
GAD	Generalised Anxiety Disorder
GCP	Good Clinical Practice
GP	General Practitioner
HRA	Health Research Authority
IAPT	Improving Access to Psychological Therapies
ICF	Informed Consent Form
ICH	International Conference on Harmonisation
ISF	Investigator Site File
MHRA	Medicines and Healthcare products Regulatory Agency
NHS R&D	National Health Service Research & Development
NIHR	National Institute for Health Research
PCMIS	Trust electronic patient record
PI	Principal Investigator
PIS	Participant Information Sheet
PWP	Psychological Wellbeing Practitioner
REC	Research Ethics Committee
SAE	Serious Adverse Event
SAR	Serious Adverse Reaction
SDV	Source Data Verification
SOP	Standard Operating Procedure
TMF	Trial Master File
WASA	Work and Social Adjustment Scale
WHO	World Health Organisation

